5.3 Measures

The putative outcome measures for baseline and follow-up assessments have been selected after consulting the Delphi report from International Committee for Harmonization of Outcome Measures for Personality Disorder (http://www.netscc.ac.uk/hsdr/files/project/SDO_FR_08-1404-083_V0_1.pdf). The f-RCT will investigate the acceptability and appropriateness of these measures for a future d-RCT which include, at screening/pre-randomisation: SCID-II PQ-BPD;

SCID-II DSM-V (BPD module); KIDSCREEN10; Pathways to Care and Demographics. Post randomisation: Mini International Neuropsychiatric Interview (MINI) 7.0.2 (18yrs+) and the Mini International Neuropsychiatric Interview (MINI-KID) 7.0.2 (under 18yrs); Adverse Childhood Experiences Scale; Autism Symptoms adolescents (ASSERT); Adult ADHD Self-Report Scale (ASRS). Baseline and follow-up: Borderline symptoms list (BSL-23); Sheehan's Disability Scale (SDS); Difficulties in Emotional Regulation Scale-SF; Patient Health Questionnaire-9; Quality of Life Questionnaire (EQ-5D); ICECAP-A; Suicidal Ideation Scale; Vocational and Educational functioning.

All the measures will be incorporated into a user-friendly questionnaire “book” and participants will have the option of completing on paper, in a telephone interview, or a mixture – a technique that has worked well in previous studies. These measures will be conducted, blind to group status, before and 12 and 24 weeks post randomization.

Analyses carried out in the f-RCT will remain blinded. Recruitment, retention rates and the BRIDGE sessions attended will be calculated with 95% confidence intervals (CI). A simple descriptive analysis of recruitment / retention relative to eligible / approached population will be conducted. While underpowered, between-group change in each measure after adjustment for baseline will be estimated using analysis of covariance (ANCOVA).

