5.1.2 Intervention

Brief, intensive assessment and integrated formulation (BRIDGE) intervention development has been guided by a) the emerging evidence base for Cognitive Analytic Therapy (CAT) with young people (age 15-25) with BPD in an early intervention service and b) in collaboration with an established Glasgow intervention programme, called Intensive Support and Monitoring Service (ISMS), used in the Glasgow youth justice system. ISMS has the explicit focus of reaching a shared formulation with the young person and the multi-agency system that supports them.

BRIDGE is delivered over 3-6 months and has a three-fold focus:

Firstly, an intensive (post-randomisation) assessment, taking up to two sessions, including BPD symptoms, copresenting difficulties, neurodevelopmental profile, life events history and psychosocial functional impact.

Secondly, up to 16 sessions of Cognitive Analytic Therapy (CAT).

Thirdly, development of a shared formulation with a multi-agency group; further development of the shared formulation with the young person, using CAT principles (Reformulation, Recognition and Revision) and, where clinically applicable, their family and service-providers.

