5.1.3 Comparison

For participants randomised to Service-As-Usual (SAU), a routine letter of their participation will be shared with their service provider(s), including the GP. SAU, likely to range from social services, mental-health services, forensic services to no intervention will be mapped and described for each participant. Treatment fidelity to SAU will therefore not be assessed, but the nature and intensity of SAU in different contexts will be described in detail through the qualitative process evaluation.

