6.3 Number of participants

A formal sample size calculation is not appropriate for this feasibility trial: Our pilot work suggests that the sample size (N=60) and timescale for recruitment and randomisation, intervention delivery and for follow-up data collection is appropriately estimated. The sample of the feasibility study is adequate to estimate clinical parameters of recruitment and retention. We will use the standard deviations of the putative outcome measures used in this study for the power calculations for the definitive RCT.

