11.1 Assessment of Safety

For all participants the NHS GGC risk management procedures will be followed and risk assessments will be carried out prior to study visit. For participants held within clinical teams (example, CAMHS), this will be done in collaboration with the participant's clinical team. For participants who may have no service involvement, NHS GGC care planning and safety

procedures will be followed with GP's as point of contact. Participants will also be told if they disclose any risk to themselves or others, we are obligated to share this with their mental health professional/GP. The core research team (trial manager, PhD student, trial therapists) will receive training on risk assessment and management as the ACADEMIC CAMHS team is embedded with specialist children's services, NHS GGC.

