12.2 Sample size

Sixty young people aged 14-24 screening for early BPD, will be randomised in a 1:1 ratio to receive either a) the brief intervention plus service-as-usual or b) service-as-usual alone. Follow up will be 12 weeks and 24 weeks post-intervention. This sample size is adequate to estimate clinical parameters for recruitment and retention. Standard deviations of the putative outcome measures will facilitate power calculations for a future d-RCT.

13 Analysis

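### If outcomes vary by BRIDGE therapist, the planned ANCOVA will understate the uncertainty of the between-group estimates, and sizing the definitive trial from standard deviations alone will make it too small

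*Combined protocol and SAP*

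**What the plan says.** The comparison of outcome measures is a baseline-adjusted ANCOVA, stated in the Synopsis, in 5.3 and in 13.2: "While underpowered, between-group change in each measure after adjustment for baseline will be estimated using analysis of covariance (ANCOVA". None of these places mentions therapist, clustering or an ICC.

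The BRIDGE arm receives "up to 16 sessions of Cognitive Analytic Therapy (CAT" (5.1.2). Section 11.1 shows that trial therapists belong to the study team: "The core research team (trial manager, PhD student, trial therapists) will receive training on risk assessment and management". Their number and caseloads are not given. The comparator is described differently in 5.1.3: "SAU, likely to range from social services, mental-health services, forensic services to no intervention will be mapped and described for each participant".

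On size, 12.2 says: "Sixty young people aged 14-24 screening for early BPD, will be randomised in a 1:1 ratio". Section 6.3 adds: "A formal sample size calculation is not appropriate for this feasibility trial". It then says that the standard deviations observed here will be used to power the definitive trial. Section 5.1 makes helping to size that trial one purpose of this study. A detailed SAP is still to be finalised (13.1 and 13.2).

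**The concern.** Participants treated by the same therapist over a course of up to 16 sessions may have outcomes more alike than those of participants treated by different therapists. Only the BRIDGE arm is described as having this structure, which makes the design partially nested. ANCOVA with independent errors ignores it.

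Two things are at stake. The first is the precision attached to the between-group estimates. The second, which matters more for a feasibility trial, is the input to the next trial: a standard deviation alone does not carry the therapist component of variance, so a calculation built only on it would come out too small if that component exists. A SAP written later can change the model, but it cannot use a link between participant and therapist that was never recorded.

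**Working it through.** **Nothing to reproduce.** The plan gives no power, effect size or target precision; N = 60 rests on pilot work (6.3). The check therefore asks how much ignoring therapists could matter.

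**Inputs from the documents.** 60 participants at 1:1, so 30 per arm (12.2); ANCOVA without a therapist term (5.3, 13.2); therapists in the plural (11.1).

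**Assumptions, because the documents give no figure.** 2, 3 or 6 therapists with equal caseloads m = 30/k, that is 15, 10 or 5; ICC of the baseline-adjusted outcome from 0 to 0.10; equal total variance in both arms; no clustering in SAU.

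**Formulas.**
- Design effect in the BRIDGE arm: DE = 1 + (m − 1) × ICC.
- Variance of the difference: DE/30 + 1/30, against 2/30 under independence.
- Ratio of true to reported standard error: √((DE + 1)/2).
- Ratio of required N at the same caseload: (DE + 1)/2.

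| Therapists (m) | ICC | DE | SE ratio | N ratio |
|---|---|---|---|---|
| any | 0 | 1.00 | 1.00 | 1.00 |
| 6 (5) | 0.01 | 1.04 | 1.01 | 1.02 |
| 6 (5) | 0.05 | 1.20 | 1.05 | 1.10 |
| 6 (5) | 0.10 | 1.40 | 1.10 | 1.20 |
| 3 (10) | 0.01 | 1.09 | 1.02 | 1.045 |
| 3 (10) | 0.05 | 1.45 | 1.11 | 1.225 |
| 3 (10) | 0.10 | 1.90 | 1.20 | 1.45 |
| 2 (15) | 0.01 | 1.14 | 1.03 | 1.07 |
| 2 (15) | 0.05 | 1.70 | 1.16 | 1.35 |
| 2 (15) | 0.10 | 2.40 | 1.30 | 1.70 |

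Worked for the last row: DE = 1 + 14 × 0.10 = 2.40; √(3.40/2) = 1.30; 3.40/2 = 1.70. Clustering also slightly lowers the expected pooled variance; allowing for that moves 1.30 to 1.32.

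**Check by simulation.** Plain ANCOVA with 30 per arm, an assumed baseline correlation of 0.5 and 20,000 runs. If a nominal 95% interval were reported, its coverage with 3 therapists would be 94.9% at ICC 0, 93.8% at 0.02, 92.7% at 0.05 and 90.1% at 0.10. At ICC 0.05 it would be 91.1% with 2 therapists and 94.0% with 6. These agree with the formula.

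**Illustration for the definitive trial.** Assume a standardised difference of 0.4, 90% power and two-sided 5%. Ignoring therapists gives 132 per arm, 264 in total. With 10 participants per therapist:
- ICC 0.02: 132 × 1.09 = 143.9, so 144 per arm and 288 in total.
- ICC 0.05: 132 × 1.225 = 161.7, so 162 per arm and 324 in total.
- ICC 0.10: 132 × 1.45 = 191.4, so 192 per arm and 384 in total.

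**Could this trial supply the ICC?** No. With 3 therapists of 10 participants each and a true ICC of 0.05, the middle 95% of simulated estimates runs from −0.11 to 0.36, and 47% are zero or negative.

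**The case against.** The case against is substantial, and much of it limits the point.

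- **The size is assumed.** The documents give no therapist number, caseload or ICC. At ICC 0 nothing changes, and the upper figures need 2 therapists and ICC 0.10 together. This stands, so the result is conditional and shown as a range from zero.
- **No ANCOVA interval or test is specified.** The 95% intervals in 5.3 and 13.2 are attached to recruitment, retention and sessions attended. A reader might infer that the plan runs a 5% test with an inflated false-positive rate; it proposes no such test. What remains is that an estimate called underpowered will need some measure of uncertainty, and that measure should not be too small.
- **Nothing decisive rests on it.** Recruitment and retention are primary, and no progression decision is tied to the ANCOVA. This stands.
- **SAU may cluster too.** Recruitment runs through local services (5.1.1), so SAU participants may share providers, and BRIDGE participants also receive SAU. The documents neither establish nor exclude this; the formula sets it to zero.
- **The SAP is still to come, and silence is not refusal.** Table 1 in 7.2 lists no therapist identifier, but delivery costs and sessions attended will be collected, so the link may exist in those records. It is not open to a reader to conclude that the plan has decided against recording it. Nor does 6.3 say that an ICC will be left out; it simply names standard deviations and nothing else.
- **The definitive trial need not keep these caseloads.** This also stands. The percentages for N apply only at the same caseload.

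**Conclusion.** The point holds in conditional form. BRIDGE is therapist-delivered, SAU is not described that way, the planned model ignores this, and the only stated input for the definitive trial is the standard deviations. If outcomes vary by therapist, the true standard error of the between-group difference exceeds the reported one by up to about 30%, and by about 1% at the mild end (6 therapists, ICC 0.01). At the same caseloads the definitive trial would need up to about 70% more people. Both ranges start at zero and rest on 2 to 6 therapists, ICC 0 to 0.10, equal caseloads and no clustering in SAU.

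A reader might go further and conclude that the intervals are too narrow as a matter of fact, that only a few therapists are involved, or that the feasibility findings are compromised. The documents support none of these: they give only a plural for therapists and no evidence on the ICC, and the recruitment and retention rates do not come from this model. This is an inexpensive improvement worth making, mainly for the sake of the next trial.

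**What to change.** 1. **Data collection (7.2).** Record the treating therapist for each BRIDGE participant, and report the number of therapists and their caseloads.
2. **Main analysis (13.2 and the SAP).** Add one sensitivity presentation, for the main putative outcome measures, of the between-group interval under a partially nested design effect over an assumed ICC range, for example 0 to 0.10. The SAP should name those measures. Repeating it for all eight baseline and follow-up measures at two follow-ups and three ICC values would add 8 × 2 × 3 = 48 intervals for little gain. Do not rely on an ICC estimated from this trial.
3. **Number of participants (6.3).** State that the definitive-trial calculation will use the standard deviations together with a therapist design effect in the BRIDGE arm, based on an external ICC range and that trial's own planned caseload.

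The cost is one data field and a few sentences. The downside is somewhat wider intervals and a larger projected definitive trial. The therapist field should come first, since the other two changes can be made later but a missing link may be hard to reconstruct.

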5.4 Process evaluation

Case-study methodology will be used to understand individual contexts, involving qualitative interviews with fourteen young people and, where possible, their parents and relevant service providers. Topics will include acceptability of the three elements of BRIDGE, perceived mechanisms of change and exploration of requirements for data collection for a future d-RCT, including for future health economic evaluation.

5.5 Health economics

For the economic analysis, data will be collected on cost of delivering the intervention in addition to participant use of health, personal social services and broader educational and societal resources.

A minimum data set of care pathways will be described at baseline and follow-up for all participants, for the purposes of future modelling of health economics impacts, in relation to putative quality of life and functional outcomes measures.

6 Recruitment details

6.1 Centre and Investigator selection

This is a multi-site trial, with trial office located at the Department of General Practice within the University of Glasgow. The following documents will be in place and copies available in the Trial Master File before recruitment of participants:

- A signed Study Agreement (CI and sponsor signature)
- The approval from the Centre's R&D Department, or organisational approval from non NHS organisations
- Completed Signature List and Roles and Responsibilities document
- Completed contacts list of all site personnel working on the Study
- Consent/assent form and PIS on letter headed paper

The NHSGG&C is included as an identified site for this study as patient notes held by the NHSGG&C will be accessed by the trial team. If remote data collection/therapeutic work is not an option for participants, they will be offered the opportunity to meet at an easily accessible location (e.g. GP surgery or public library). We will follow all local Covid guidance e.g. a phone call will be made to ensure that the participant is feeling well and has no symptoms prior to attending the appointment.

6.2 Trial population

Sixty young people aged 14-24 screening for early BPD, will be randomised in a 1:1 ratio to receive either a) the brief intervention plus service-as-usual or b) service-as-usual alone. Follow up will be 12 weeks and 24 weeks post-intervention. This sample size is adequate to estimate clinical parameters for recruitment and retention. Standard deviations of the putative outcome measures will facilitate power calculations for a future d-RCT.

6.2.1 Inclusion Criteria

- Cut off score of 11 out of 15 on the self-reported SCID-II BPD questionnaire (at screening 1 - see below) AND sub-threshold (3 or 4 out of 9 domains) or threshold (5 and above out of 9 domains) criteria on the SCID-II DSM-V for BPD.
- Aged between 14 and 24 years, until their 25th birthday

6.2.2 Exclusion criteria

Young people meeting the following criteria will be excluded:

- Currently receiving psychological/counselling /psychotherapeutic treatment for BPD
- Has received any previous psychological for Borderline Personality Disorder (BPD)/BPD Symptoms
- Receiving intensive psychiatric treatment at the time of study entry, for conditions such as acute psychosis or severe eating disorder
- Non-English speaking

6.3 Number of participants

A formal sample size calculation is not appropriate for this feasibility trial: Our pilot work suggests that the sample size (N=60) and timescale for recruitment and randomisation, intervention delivery and for follow-up data collection is appropriately estimated. The sample of the feasibility study is adequate to estimate clinical parameters of recruitment and retention. We will use the standard deviations of the putative outcome measures used in this study for the power calculations for the definitive RCT.

6.4 Recruitment and informed consent

Participants can be either referred by a professional in a range of settings in Glasgow (for example, CAMHS, Social work, counsellors) or can self-refer by completing an online or paper screening assessment, the brief (15-item) SCID-II PQBPD questionnaire.

Participants are being recruited from the general population, posters and leaflet's advertising the study will be disseminated at healthcare centres and other key sites guided by our PPI group. Social media and public transport will also be key areas of advertisement for the study.

Participants who express interest in the study to their referring practitioner or those who self-refer from study publicity will speak to a member of the trial research team. During this call, the participants will be invited to complete a screening questionnaire to determine eligibility for the study.

Following referral, and prior to completion of the eligibility screening form (online or paper format), the trial research team (trial manager and research associate) will ensure eligible adolescents and young people receive the study 'Participant Information Leaflet'. At least 24 hours later, the research team will contact the young person to discuss the study further and seek consent. Informed consent from young people (14-24), and consent from parents of children (age 14-16 who are judged by a healthcare professional as incapable of providing

consent) will be obtained as well as assent from the child. Information, consent and assent procedures will be developed further with input from the first PPIe workshop and in consultation with the Study Steering Committee (SSC). Any consent forms in paper form will be stored at the University of Glasgow trial office in locked cabinets in the rooms with access limited to the research team. No one outside of the research team or appropriate governance staff will be able to find out participant's details, or any other information which could identify them. Any consent forms held electronically will be stored in a secure, password protected study specific folder that is located on the university server facilities with access limited to the study team only. Access to information held on University computers will be password protected. Data will be held for 10 years after the study has been completed, as per the applicable data security and management protocol.

7 Data Collection

All qualitative data will be collected by the experienced researchers trained in the administration of the qualitative interviews. The data will be recorded on the recommended audio recording equipment (e.g. encrypted voice recorders), transcribed in house and digital format of the transcripts stored securely in the electronic study files located on the secured University IT infrastructure.

All quantitative data will be collected via data collection forms developed by the trial team. The study will have data collection system allowing collection of participant's research data where participant will be identified with the study specific participant number only.

7.1 Confidentiality of personal data

The study team works in line with General Data Protection Regulations (2018). All participants will be identified by a study specific number. No names or other personal identifiers will be used in data collection forms. Since name and address information are needed for participant's follow up, the research team will use a master list matching study identifiers to this personal information. However, this list will be password protected, used only by the immediate study team and be kept in a study file accessible to only study team on a secure server within Research Institution. This information as indicated above will be kept separate from the research data, which constitute the research outputs of this study. Copies of consent forms will be kept in a locked filing cabinet in an office with a limited access to research team only. All assessment and questionnaire forms will only bare study specific ID number. Audio recordings will not directly address participants by their names but rather study specific number. Any personal details and any other identifying

characteristics will be removed before being stored in password protected file accessible by the research team only on secured University Servers or the secure trial MS Teams page

7.2 Data Collection forms

A user-friendly booklet will be developed by the trial team incorporating relevant demographic and health economic information, as well as the following psychometrics:

Table 1. Baseline and follow-up assessments for the feasibility trial (The BRIDGE project)

Measure*	Baseline	12 wks	24 wks	What measuring?
Questionnaires				
SCID-II PQ-BPD	✓	✓	✓	BPD symptoms (self-reported)
SCID-II DSM-V (BPD module)	✓	✓	✓	BPD criteria (>3 or above out of 9 domains)
KIDSCREEN10	✓	✓	✓	Overall Functioning
Care pathways record and minimum data set	✓			Demographics, pathways to care
Questionnaires				Intensive assessment (BRIDGE)
K-SADS/PL	✓			Assessment of lifetime and present psychopathology
Adverse Childhood Experiences Scale	✓			Adverse childhood experiences
Autism Symptoms adolescents (ASSERT)	✓			Autism assessment
Adult ADHD Self-Report Scale (ASRS)	✓			ADHD symptom checklist
Putative outcome measures of change				Possible mechanisms of change
Borderline symptoms list (BSL-23)	✓	✓	✓	BPD symptom severity
Sheehan's Disability Scale (SDS)	✓	✓	✓	Functioning: work/school, social and family life
Difficulties in Emotional Regulation Scale-SF	✓	✓	✓	Domains of emotional regulation
Patient Health Questionnaire-9	✓	✓	✓	Severity of depression
Quality of life Questionnaire (EQ-5D)	✓	✓	✓	General health related quality of life

ICECAP-A	✓	✓	✓	Wellbeing assessment (Economic Evaluation)
Suicidal Ideation Scale	✓	✓	✓	Suicidal thinking and behaviours (ideation, self-harm, attempts)
Vocational and Educational functioning	✓	✓	✓	School and work (Paid and Unpaid) engagement

* The outcome measures for baseline and follow-up assessments have been selected after consulting the Delphi report from International Committee for Harmonization of Outcome Measures for Personality Disorder (http://www.netscc.ac.uk/hsdr/files/project/SDO_FR_08-1404-083_V01.pdf)

8 Randomisation

Randomisation will be controlled by the Trial Team at the University of Glasgow, who will randomise participants (1:1) to BRIDGE (+SAU) or SAU (see section 10). The trial manager will generate a randomisation list to ensure data collector blindness. The randomisation list will be stored in a password protected file within the Trial Team's private Microsoft Teams channel, and access will be restricted only to those members of the research team who will remain unblinded throughout the study. A log of access will be maintained.

9 Withdrawal & loss to follow-up

Participants have the right to withdraw consent for participation in any aspect of the BRIDGE trial at any time. The participants care will not be affected at any time by declining to participate or withdrawing from the trial.

A participant may withdraw or be withdrawn from the intervention for the following reasons:

- Withdrawal of consent by participant request
- Any alteration in the participants condition or circumstances which justifies the discontinuation of the intervention in the investigators opinion

If a participant is to be withdrawn, a discussion will take place with the participant – and if necessary with his/her legal representative. The data collected till the point of withdrawal will be retained and this will be clearly documented in participant information sheet and consent form.

The research team will complete a withdrawal form for all participants who consent and subsequently withdraw. This withdrawal form will be retained in the study file. Any queries relating to potential withdrawal of a participant should be forwarded to the Trial Manager.

Upon recruiting participants to the trial, we will gather contact information for them and will explain the plans for future contact. The study does not involve a long period of contact with participants, and therefore we do not expect to lose contact with a high proportion of participants. One of the aims of this study is to determine retention rates.

10 Intervention

Brief, intensive assessment and integrated formulation (BRIDGE) intervention development has been guided by a) the emerging evidence base for Cognitive Analytic Therapy (CAT) with young people (age 15-25) with BPD in an early intervention service and b) in collaboration with an established Glasgow intervention programme, called Intensive Support and Monitoring Service (ISMS), used in the Glasgow youth justice system. ISMS has the explicit focus of reaching a shared formulation with the young person and the multi-agency system that supports them.

BRIDGE is delivered over 3-6 months and has a three-fold focus:

- 1) An intensive (post-randomisation) assessment, taking up to two sessions, including BPD symptoms, co-presenting difficulties, neurodevelopmental profile, life events history and psychosocial functional impact.
- 2) Up to 16 sessions of Cognitive Analytic Therapy (CAT).
- 3) Development of a shared formulation with a multi-agency group; further development of the shared formulation with the young person, using CAT principles (Reformulation, Recognition and Revision) and, where clinically applicable, their family and service-providers.

For participants randomised to Service-As-Usual (SAU), a routine letter of their participation will be shared with their service provider(s), including the GP. SAU, likely to range from social services, mental-health services, forensic services to no intervention will be mapped and described for each participant. Treatment fidelity to SAU will therefore not be assessed, but the nature and intensity of SAU in different contexts will be described in detail through the qualitative process evaluation.

11 Safety Reporting

